## **6.5 Sample Size and Power**

A sample size of 50 in each group (total N = 100) will have 80% power to detect a moderate effect size of 0.566 using a two group t-test with a 0.05 two-sided significance level. We plan to recruit 70 in each group to account for attrition.

# **7 SAFETY MANAGEMENT**

## **7.1 Clinical Adverse Events**

Clinical adverse events (AEs) will be monitored throughout the study.

## **7.2 Adverse Event Reporting**

All on-site SAEs (CHOP or related sites) will be reported to the IRB in accordance with CHOP IRB policies. AEs that are not serious will be summarized in narrative or other format and submitted to the IRB at the time of continuing review.

## **7.3 Definition of an Adverse Event**

An adverse event is any untoward medical occurrence in a subject who has received an intervention (drug, biologic, or other intervention). The occurrence does not necessarily have to have a causal relationship with the treatment. An AE can therefore be any unfavorable or unintended sign (including an abnormal laboratory finding, for example), symptom, or disease temporally associated with the use of a medicinal product, whether or not considered related to the medicinal product.

All AEs (including serious AEs) will be noted in the study records and on the case report form with a full description including the nature, date and time of onset, determination of non-serious versus serious, intensity (mild, moderate, severe), duration, causality, and outcome of the event.

## 7.4 Definition of a Serious Adverse Event (SAE)

An SAE is any adverse drug experience occurring at any dose that results in any of the following outcomes:

- death,
- a life-threatening event (at risk of death at the time of the event),
- requires inpatient hospitalization or prolongation of existing hospitalization,
- a persistent or significant disability/incapacity, or
- a congenital anomaly/birth defect in the offspring of a subject.

Important medical events that may not result in death, be life-threatening, or require hospitalization may be considered a serious adverse drug event when, based upon appropriate medical judgment, they may jeopardize the subject and may require medical or surgical intervention to prevent one of the outcomes listed in this definition.

A distinction should be drawn between serious and severe AEs. A severe AE is a major event of its type. A severe AE does not necessarily need to be considered serious. For example, nausea which persists for several hours may be considered severe nausea, but would not be an SAE. On the other hand, a stroke that results in only a limited degree of disability may be considered a mild stroke, but would be an SAE.

### 7.4.1 Relationship of SAE to study drug or other intervention

The relationship of each SAE to the study intervention should be characterized using one of the following terms in accordance with CHOP IRB Guidelines: definitely, probably, possibly, unlikely or unrelated.

## 7.5 IRB/IEC Notification of SAEs and Other Unanticipated Problems

The Investigator will promptly notify the IRB of all on-site unanticipated, serious Adverse Events that are related to the research activity. Other unanticipated problems related to the research involving risk to subjects or others will also be reported promptly. Written reports will be filed using the eIRB system and in accordance with the timeline below. External SAEs that are both unexpected and related to the study intervention will be reported promptly after the investigator receives the report.

Type of Unanticipated Problem	Initial Notification (Phone, Email, Fax)	Written Report
Internal (on-site) SAEs Death or Life Threatening	24 hours	Within 2 calendar days

Internal (on-site) SAEs All other SAEs	7 days	Within 7 business days
Unanticipated Problems Related to Research	7 days	Within 7 business days
All other AEs	N/A	Brief Summary of important AEs may be reported at time of continuing review

### 7.5.1 Follow-up report

If an SAE has not resolved at the time of the initial report and new information arises that changes the investigator's assessment of the event, a follow-up report including all relevant new or reassessed information (e.g., concomitant medication, medical history) should be submitted to the IRB. The investigator is responsible for ensuring that all SAE are followed until either resolved or stable.

### 7.6 Investigator Reporting of a Serious Adverse Event to Sponsor

Reporting must be consistent with regulatory, sponsor or GCRC requirements (if applicable)

### 7.7 Medical Emergencies (if applicable)

Conditions that will generate an Urgent Medical Referral (UMRA) are those laboratory, physiological or behavioral findings that are believed to represent conditions that may require additional evaluation by the participant's health care providers in a timely manner. Thus, if these conditions are identified during the course of the study, their occurrence will generate an Urgent Medical Referral by the PI who will communicate with the participant's guardian, and with his permission will contact the child's primary care provider. These conditions include:

- Subjects with significant hypoxemia on polysomnography ( $> 10\%$  of total sleep time with  $S_pO_2 < 75\%$ )
- Subjects with severe OSAS-related arrhythmias on polysomnography.

## 8 STUDY ADMINISTRATION

### 8.1 Data Collection and Management

1. Confidentiality. Data will be stored in a password-protected file stored on the sleep secure research server. Sleep study data will be backed up on CD/DVDs and stored in a locked cabinet. The video recordings are part of the sleep study, and as such they will be kept forever, stored in a locked office in the sleep lab with restricted access.
2. Security. Data will be backed up in Redcap as a copy of the password-protected file on the PI's office computer.

---

3. Anonymization, de-identification or destruction. The identifiers will be destroyed after publication. However, identifiers of subjects who have agreed to be contacted for future research will be kept in a password protected file. The other data will be retained forever. Our laboratory maintains a locked cabinet specifically for such archives.

## **8.2 Confidentiality**

All data and records generated during this study will be kept confidential in accordance with Institutional policies and HIPAA on subject privacy. The Investigator and other site personnel will not use such data and records for any purpose other than conducting the study. Research data and records will be saved as password-protected computer files. Patient identifiers will be removed. Data will be stored indefinitely. The Investigators will not use such data and records for any purpose other than conducting the study.

No identifiable data will be used for future study without first obtaining IRB approval. The investigator will obtain a data use agreement between provider (the PI) and any recipient researchers (including others at CHOP) before sharing a limited dataset (dates and zip codes).

## **8.3 Regulatory and Ethical Considerations**

### **8.3.1 Data and Safety Monitoring Plan**

- Principal Investigator: It is the responsibility of the Principal Investigator to oversee the overall safety of the study. This will include careful assessment and appropriate reporting of adverse events. The PIs responsibility will be to assure that appropriate study data are communicated to the participant's family and physicians and that appropriate referrals or interventions are initiated. He will discuss AEs with the medical monitor and report them to the IRB, DSMB and NIH when appropriate.
- Medical Monitor: [name] will be the medical monitor with whom the team will discuss AEs. She is otherwise unrelated to the research protocol and will not perform research procedures, as mandated by NHLBI.
- Data Safety Monitoring Board (DSMB): The study will have a Data Safety Monitoring Board (DSMB) as mandated by NHLBI. The DSMB will be responsible for overall participants' safety during the study. DSMB members are experts in their field, have bioethical experience in conducting research in children, and are unrelated to this research. The DSMB will be comprised of:
  - [name]. Professor of Pediatrics, Albert Einstein College of Medicine. Chief, Division of Respiratory and Sleep Medicine, Montefiore Medical Center. [name] is the external member of the DSMB.
  - [name], Attending Physician, Division of Otolaryngology, The Children's Hospital of Philadelphia

---

- [name]. Biostatistician. The Children's Hospital of Philadelphia Clinical and Translational Research Center.
- The DSMB will meet twice a year and as needed. The meetings will be held via teleconference. Serious adverse events and unanticipated events will be reported according to NHLBI policies. Once a month, the DSMB will receive reports of all adverse events (AE). On a quarterly basis, or more frequently if needed, summary reports of all AEs will be provided to the DSMB. For each DSMB meeting, reports will be provided. These will include data on recruitment and baseline characteristics, completeness of follow-up, and analyses of AEs. [name], the study statistician, will prepare these reports. The reports will provide information that is accurate, with follow-up that is complete to within one month of the date of the DSMB meeting. The reports will be provided to DSMB members approximately one week prior to the date of the meeting. Minutes for each meeting will be prepared.

### 8.3.2 Risk Assessment

**Polysomnography:** Not greater than minimal risk. No significant risks are encountered from polysomnography, which is a standard, noninvasive monitoring procedure. Sleeping away from home may be unsettling. To allay anxiety, the subject's parents/guardians will be allowed to stay overnight in the same room as the subject. The subjects may develop skin rashes as a result of adhesive tapes.

**Diffuse optical and correlation spectroscopy:** Not greater than minimal risk. The hybrid DOS/DCS instrument is considered a non-significant risk device. There has been experience at both CHOP and The Hospital of the University of Pennsylvania with the instrument, and there have been no AEs. Please see attached safety notes.

**Psychometric Testing:** Not greater than minimal risk. This testing is potentially stressful or anxiety-producing; these risks will be addressed by offering breaks from testing as needed and having examiners who are well-trained in testing children and adolescents. Testing will be conducted in an appealing and quiet private area with child-sized furniture.

**Hypercapnic challenge:** Not greater than minimal risk. During wakefulness, the measurement of carbon dioxide and hypoxic responses may make the participant feel short of breath, as if he/she was running. Rarely, the participant may have a headache or dizziness from increased carbon dioxide. This will go away quickly after the test or after coming off the mouthpiece. The subject can come off the mouthpiece if he/she is uncomfortable. During sleep, these tests may cause arousal; typically, the subject is unaware of the cause of the arousal, and rapidly returns to sleep. If the participant is uncomfortable, s/he simply needs to remove the mask in order to breathe room air. The test will be stopped if the subject has frequent arousals, defined as waking from sleep more than 3 times during the hypercapnic challenge). A physician will be present whenever CO2 is administered, and the subject's end-tidal and transcutaneous PCO2, arterial oxygen saturation, EKG and EEG will be continuously monitored. Sleep disruption from arousals may result in excessive daytime sleepiness, inattention and impaired vigilance the following day. These effects are transitory and resolve with a good night of sleep. (35) Therefore, participants should not take school tests the following day.

---

**Physical exam:** Participants may experience momentary embarrassment or discomfort, but this is unlikely. This brief exam is similar to exams that children normally have as part of their regular medical care.

**Medical history, interviews and record reviews:** As with any study that involves collecting data, it is possible that someone who is not involved with the study may get access to participants' confidential information. Every precaution will be taken to secure participants' personal information to ensure confidentiality. At the time of participation, each participant will be assigned a study identification number. This number will be used on data collection forms and in the study database instead of names and other private information. A separate list that links each participant's name to the study identification number will be maintained for future reference and communication.

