##### **3.3.1.2 Control Subjects**

The study will include 7 total visits for controls: a baseline sleep study to ensure normalcy, three full days of cognitive and behavioral and CBF testing (baseline, 6 and 12 months), and three sleep studies with CBF testing (baseline, 6 and 12 months). A daytime visit and one night time visit may be scheduled during a 24-hour period if the participant and family wish so. Otherwise, they will be scheduled on separate days.

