## 4 STUDY PROCEDURES

### 4.1 OSAS Participants

#### 4.1.1 Screening Visit + Visit 1

The following procedures will be performed:

- Informed consent will be obtained before any study procedure/evaluations occur
- Review of inclusion/exclusion criteria
- Administer ABAS-III
- Demographics and medical history
- Mallampati/tonsillar size assessment
- Height and weight assessment
- OSAS participants will undergo a sleep study only if this has not been obtained clinically during the previous 12 months.
- OSAS participants will undergo a sleep study with CBF testing if a diagnostic sleep study has already been performed to confirm OSAS.

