#### 4.1.2 Visit 2: Daytime, 1 to 30 days after screening visit

- Mallampati airway score and tonsillar assessment
- Cognitive and behavioral testing
- CBF testing during wakefulness during hypercapneic ventilatory response

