#### 4.1.5 Visit 5: Nighttime, 6 months after adenotonsillectomy

- CBF testing during sleep during hypercapneic ventilatory response

- Height and weight assessment

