**4.2.3 Visit 3: Nighttime, 1 to 30 days after screening visit**

- Height/weight assessment
- CBF testing during sleep during hypercapneic ventilatory response

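### The schedule lets OSAS children take the baseline attention tests the day after a CO2-challenge night, and the listed visit order concentrates that exposure in one group at one time point

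*Combined protocol and SAP*

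**What the plan says.** On the effect of the challenge night, Section 8.3.2 states: "Sleep disruption from arousals may result in excessive daytime sleepiness, inattention and impaired vigilance the following day". It adds that these effects pass after a good night's sleep, and it advises against school tests on the day after.

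On OSAS baseline, Section 4.1.1 states: "OSAS participants will undergo a sleep study with CBF testing if a diagnostic sleep study has already been performed to confirm OSAS". The footnote to Table 1 merges Screening and Visit 1 for these children. Section 3.1 makes a prior clinical study the usual route, except for PeRC referrals. The cognitive battery and awake CBF testing are at "Visit 2: Daytime, 1 to 30 days after screening visit".

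On OSAS follow-up, the day visits (4 and 6) are numbered before the night visits (5 and 7), for example "Visit 5: Nighttime, 6 months after adenotonsillectomy". Each pair shares one nominal time.

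On controls, the screening night is a sleep study listed without CBF testing. Cognitive testing is Visit 2, and the CO2 night is "Visit 3: Nighttime, 1 to 30 days after screening visit", with the same window as Visit 2. Section 3.3.1.2 adds: "A daytime visit and one night time visit may be scheduled during a 24-hour period if the participant and family wish so". It does not say which comes first.

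On analysis, Section 6.3 provides a tester blinded to group. Section 6.4.2 names age, gender, race, socio-economic status and BMI as potential confounders. Neither visit order nor time since the challenge night is named.

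**The concern.** The protocol accepts that a challenge night can impair attention and vigilance the next day. The battery in Section 5.1.3 measures those functions (the CPT, TEA-Ch and Digit Span). The protocol protects school tests but not its own outcome measures.

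As the visits are listed, only OSAS baseline testing follows a challenge night. A temporary loss there would add to the baseline OSAS-control difference in cognition. It would then disappear at 6 and 12 months and look like recovery after surgery. The time-by-group term in the GEE models would not remove this, because an artefact present only at OSAS baseline is itself such an interaction. Blinding the tester to group does not remove it either. The exposed endpoints are the pre/post cognitive change (Section 6.2), the baseline cognitive comparison and, weakly, the correlation part of the primary endpoint (Section 6.1).

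**Working it through.** **The plan's own figure.** Section 6.5 says "A sample size of 50 in each group (total N = 100) will have 80% power" for an effect of 0.566, "using a two group t-test with a 0.05 two-sided significance level". The exact noncentral-t power at 50 per group is 80.0%, so the figure reproduces. It concerns CBF change. It is used here only for the group size of 50.

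**Listed order, side by side.**

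| Group | Baseline | 6 months | 12 months |
|---|---|---|---|
| OSAS, prior clinical study | CO2 night (1), then test day (2) | day (4), night (5) | day (6), night (7) |
| Controls | plain sleep study (1), test day (2), CO2 night (3) | day (4), night (5) | day (6), night (7) |

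**Formula.** Let f be the share of OSAS children tested the day after the CO2 night, and c the next-day decrement in SD of the cognitive score. With no such exposure among controls or at follow-up, bias = f x c. If a share g of controls is also exposed, bias = (f - g) x c. The documents give none of f, g or c, so all are assumed.

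The false-positive rates below use 50 per group, no true effect and g = 0. The paired column is the pre/post test within OSAS, with an assumed baseline/follow-up correlation of 0.5.

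| f | c (SD) | Bias (SD) | False positive, OSAS vs control | False positive, OSAS paired |
|---|---|---|---|---|
| 1/30 (even over days 1-30) | 0.2 to 0.5 | 0.007 to 0.017 | 5% | 5% |
| 0.5 | 0.2 | 0.10 | 8% | 11% |
| 0.5 | 0.3 | 0.15 | 11% | 18% |
| 0.5 | 0.5 | 0.25 | 23% | 39% |
| 1 (upper bound) | 0.3 | 0.30 | 32% | 55% |

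With the correlation at 0.5, the group-by-time false-positive rates equal those for OSAS vs control. If a quarter of controls were also exposed (g = 0.25), the middle case would fall to (0.5 - 0.25) x 0.3 = 0.075 SD.

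**Effect on the CBF-cognition correlation (f = 0.5, c = 0.3).**
- Within OSAS, a decrement unrelated to CBF adds variance 0.5 x 0.5 x 0.3² = 0.0225. It multiplies r by 1/√1.0225 = 0.989, a loss of about 1%.
- Pooled over both groups, assume a CBF group difference of 0.566 SD. The spurious covariance is 0.25 x 0.566 x 0.15 = 0.021, so the spurious r is about 0.02. The standard error of r at N = 100 is about 0.10.

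**The case against.** The strongest objection is that the order is not fixed. Visits 4 and 5 share one nominal time, as do Visits 6 and 7, and control Visits 2 and 3 share one window. Section 3.3.1.1 describes OSAS testing in prose with day testing first at baseline and the night study first at follow-up, the reverse of Table 1. A reader might infer that carry-over must produce both the baseline deficit and its later recovery. The documents do not support that. They permit the pattern and list it in the schedule, but do not require it.

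Other objections also stand:
- The 24-hour option is written for controls and does not exclude night-then-day, so controls may be exposed too. They may also be tested the day after a plain laboratory night.
- On the CO2 night OSAS children receive positive pressure aimed at treating their apnea, which may offset some disruption. Challenges are short, with one trial per sleep stage. The net direction is likely but not certain.
- For OSAS children with a separate research screening study, Visit 1 has no stated window relative to Visit 2, so their exposure is undetermined.
- The decrement is plausible mainly for attention performance tests. The BRIEF-2, Child Behavior Checklist and ABAS-III are ratings of general behavior.

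Two further inferences should be resisted. One is that awake CBF, measured at the same visit, is also distorted; the protocol states no next-day effect on CBF. The other is to judge the bias against 0.566 SD; that is the planned CBF effect, not a cognitive one.

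What the objections leave untouched is that next-day testing is allowed for OSAS children on the usual route, that the protocol itself expects impairment that day, and that nothing in the design or analysis controls for it.

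**Conclusion.** The gap is real, and its size is unknown. The bias ranges from about 0.01-0.02 SD, if Visit 2 falls evenly over days 1-30, to 0.15 SD if half of OSAS children are tested next day with a 0.3 SD decrement. In that second case the false-positive rate for a group difference in cognition is 11% instead of 5%. These figures rest on assumed shares and decrements, no exposure among controls, and follow-up testing in the listed order. The exposed results are the baseline cognitive comparison and the pre/post cognitive change, chiefly on attention tests. The effect on the CBF-cognition correlation is small, and none is documented on the CBF group comparison. Confidence is good that the schedule permits this and low on how much it matters. It is a cheap improvement to make, not a defect that undermines the trial.

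**What to change.** In Sections 4.1.2, 4.1.4-4.1.7, 4.2.2-4.2.7 and 3.3.1.2, state one rule for both groups at all time points: cognitive testing takes place before the CO2-challenge night, or after at least one intervening night. Limit the 24-hour option to day-then-night. The rule should also cover OSAS children whose Visit 1 is separate from screening. One intervening night is enough on the protocol's own account of how quickly the effects pass.

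For children already tested, use visit dates to flag tests done the day after a challenge night, report the count by group and time point, and repeat the cognitive analyses without them.

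The change adds no visits, tests or participants, and the sample size stands. The cost is that some families lose the night-then-day option.

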### **8.3.3 Potential Benefits of Study Participation**

There will probably be no direct benefits to the individual subject. Subjects with OSAS may benefit from the follow-up polysomnography to evaluate their treatment. Control subjects may benefit if unsuspected abnormalities are detected on polysomnography.

### **8.3.4 Risk-Benefit Assessment**

The risks of this study are not greater than minimal. Although participating subjects may not obtain direct benefit, data from this study will help better understand the pathophysiology of OSAS, so that ultimately we can develop better forms of prevention and of treatment.

## **8.4 Recruitment Strategy**

Subjects with OSAS will be recruited from the Sleep Center at the Children's Hospital of Philadelphia. The Sleep Center is composed of both a Sleep Clinic and Sleep Laboratory. The multidisciplinary Sleep Clinic (pediatric pulmonology, neurology and psychology) evaluates approximately 2,000 pediatric subjects with varying sleep disorders each year; approximately half of these are referred for polysomnography.

All the care providers at the Sleep Clinic will be informed of this study. If the prospective subjects are not patients of this study's P.I., they will be notified of this study by their physician. If the subjects are interested in the study, they will be referred to us. We will also screen the results of the polysomnograms performed in the Sleep Laboratory for clinical purposes to identify more eligible subjects with OSAS. We will approach the eligible subjects with OSAS to discuss this study. In addition, we will set up a PeRC prompt in the CHOP system to facilitate the referral of children with suspected OSAS. Our team will coordinate the sleep study of these children.

Controls will be recruited from the community based in advertisements in newspaper/magazine.

---

The study team will also utilize the services of the Recruitment Enhancement Core (REC). The REC provides assistance with recruitment plan development and may assist in identifying and contacting potential participants using the Clinical Reporting Unit (CRU), the CHOP Recruitment Registry, social media and internal communication resources. The REC also engages community partners and facilitates outreach on behalf of the research Institute and CHOP research studies.

The investigators will abide by IRB SOP 15, which states that "Employees, volunteers (ie; NTP) and their immediate families may not participate in research studies within a division in which they work or are assigned, unless a waiver is granted from the IRB Chair (such as for treatment studies).

The flyer that is currently attached to the eIRB application will be the only form of print material used for newspaper and/or magazine ads.

**The Research Creative Institute has also developed a flyer to be distributed to patients which will be given to possible participants for information purposes.**

